4.0 Research Design and Methods

Describe the research design and methods and procedures to be used in achieving the specific aims of the research project. If applicable, mention the type of personal protective equipment (PPE), use of aerosol confinement, and the need for the use BSL2 or BSL3 laboratory for different part of the intended research in the methods.. Define the study population with inclusion and exclusion criteria, the sampling design, list the important outcome and exposure variables, describe the data collection methods/tools, and include any follow-up plans if applicable. Justify the scientific validity of the methodological approach (biomedical, social, gender, or environmental).

Also, discuss the limitations and difficulties of the proposed procedures and sufficiently justify the use of them.

This study is a phase II, randomized, placebo controlled, double blind efficacy and safety trial. The study is designed for the assessment of a novel fixed dose combination (FDC) drug VR-AD-1005 for the treatment of acute watery diarrhea in adult cholera patients. Adult (18-65 years) cholera patients admitted to icddr, Dhaka Hospital will be randomized to intervention and placebo groups with 75 patients per group.

Group A (intervention product arm): Patients will receive VR-AD-1005 treatment for three days, or less if recovered earlier, in addition to the general cholera protocol treatment.

[figure not shown]
Group B (placebo arm): Patients will receive placebo for three days, or less if recovered earlier, in addition to the general cholera protocol treatment.

Key aspects of the trial design and Trial Schema are given below in table 2 and figure 2.

Table 2: Key aspects of the trial design

Intervention Model: Parallel arm intervention model with 2 Arms: Group A (intervention product arm) and Group B (placebo arm)	Population Type: [Adult patient]
Control: [placebo] Intervention: [VR-AD-1005]	Population Diagnosis or Condition: [Vibrio cholerae infection]
Active Comparator: [not applicable]	Population Age: Minimum: [18y.o.] – Maximum: [65y.o.]
Trial Intervention Assignment Method: Double-blind randomization	Site Distribution: Single site

Figure 2-Trial Schema

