- Patients will receive their first dose administered by the study nurse immediately after the consenting process and randomization is completed. The treatment is in a capsule form and participants will be instructed by the study nurse to swallow the treatment whole without chewing with a glass of water or oral rehydration solution. The volume of liquid used for ingesting the treatment will be recorded in patient water intake charts for monitoring and analysis purposes. Subsequent doses will be timed based on the first dose (i.e. second dose is 3 hours after first dose). The study nurses will record the timing for each patient's medication and will keep strictly to the timing between shifts by handing over study patient folder records after each shift. Study nurses will additionally monitor for vomiting or accidental loss of treatment dose (for example, dropped dose) and to re-administer, if vomiting occurs within 30 minutes of treatment administration or if the pill is clearly visible in the vomit.
- Stool samples will be taken to the laboratory for culture and identification of *V. cholerae* and blood samples taken for study laboratory assessments. Laboratory assessments will be conducted at the icddr, Immunobiology, Nutrition and Toxicology Laboratory and/or diagnostics laboratories. Any other necessary study laboratory test may be performed at any of these laboratories depending on capacity and efficiency of study procedures.
- During the three days of admission, participants will be monitored daily by study doctors and nurses. Treatment will be given as per scheduled doses each day, monitoring and measurement of water intake, weighing of vomiting and stool output using calibrated scales (scales will be calibrated on daily basis) and all other study procedures. For recruited patients whose culture comes back negative for cholera, treatment will be stopped (culture results expected by day three) and they will not be included in the final analysis.
- In the event of SAE's during treatment or after discharge, participants will be referred to the appropriate clinic for comprehensive management.
- Participants will only be discharged when the study doctors deem so after the three days of treatment. Participants who are not discharged after 3 days will not receive further treatment but will be monitored by study staff.

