4.4.6 Participant Assignment, Randomization and Blinding

4.4.6.1. Participant Assignment

During recruitment, in addition to rehydration/antibiotics, each eligible participant will receive a numbered individual package of treatment, with package number being unique to the particular participant. After the end of the study for the purpose of data analysis the randomization tables will be supplied to the biostatisticians and data from all participants who have completed the trials will be assigned to the Group A (VR-AD-1005 intervention) or Group B (placebo) for analysis.

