4.5. Trial Assessments and Procedures

4.5.1. Screening/Baseline Assessments and Procedures

- Medical history: All patients admitted with secretory diarrhea with severe dehydration will be offered to participate in the study.
- Informed consent. Severely ill patients unable to sign the consent form will be resuscitated according to the proper SOPs, until they are able to make an informed decision regarding the enrollment.
- Randomization and assignment to treatment Group. IP assignment.
- Concomitant medication review.
- Physical examination: height, body weight, temperature, thirst, HEENT (note and record signs of dehydration, such as sunken eyes), skin (note and record signs of dehydration, such loss of turgor), level of consciousness using AVPU (active, response on voice or pain, unconscious) criteria, vomiting.
- Hydration status should be assessed in each participant including assessment of IV fluids, oral ORS intake and oral water intake.
- Vital signs: body temperature, heart rate, respiratory rate, blood pressure (including orthostatic blood pressure measurement when possible), urine output.
- Blood collection (5 ml) for Complete Blood Count (CBC), Basic Metabolic Panel (BMP) including serum electrolytes and creatinine.
- Stool collection for *V. cholerae* RDT (dark field microscopy) and culture.
- Initiate Re-hydration and antibiotic treatment in accordance with the SOPs for cholera patients until recovery.
- Initiate IP administration as soon as participants can tolerate oral intake.

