If any serious adverse events occur before treatment phase, study treatment may be postponed at the researcher's decision.

The reason for participant discontinuation or withdrawal from the study will be recorded on the CRF. Subjects who sign the informed consent form and are randomized but do not receive the study intervention may be replaced. Subjects who sign the informed consent form, and are randomized and receive the study intervention, and subsequently withdraw, or are withdrawn or discontinued from the study, will not be replaced.

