5.0 Sample Size Calculation and Outcome (Primary and Secondary) Variable(s)

Clearly mention your assumptions. List the power and precision desired. Describe the optimal conditions to attain the sample size. Justify the sample size that is deemed sufficient to achieve the specific aims.

Planned screening is 500 participants. ITT (intention to treat) group is 150 patients. Enrollment will stop once 150 participants are recruited, or once 100% of per-protocol dataset (PP) is achieved. Sample size was calculated based on the mean volume of stool output in cholera patients. Mean stool output was assumed at 280 ± 156 g/kg²²⁻²⁴. Assuming 33% reduction (alternative hypothesis) vs no reduction (null hypothesis), sample size was calculated using GraphPad Prism software for two-tailed t-test with alpha 5% and power 0.8. Using recruitment of 50 participants per arm (100 total), power level of 0.82 can be achieved. Although, this is a sufficient level of power for the projected study, data points lost due to participant drop-out, cross-over to other study arms, withdrawal and missing data will affect the power of the study. We calculated that recruitment of up to 75 patients per study arm would allow power of 0.94.

Endpoints associated with primary and secondary objectives, and justification for endpoints are given below (Table 1).

Table 1-Primary and Secondary Objectives and Endpoints

OBJECTIVES	ENDPOINTS	JUSTIFICATION FOR ENDPOINTS
Primary		

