Number of unscheduled IV rehydration episodes per treatment. The number of unscheduled IV rehydration episodes per treatment will be recorded for the entire duration of the treatment. Unscheduled IV rehydration is defined as "receipt of IV fluid during the maintenance phase of hydration due to development of severe dehydration or some dehydration with high purging (>15 ml/kg/hour) or persistent vomiting (>3 episodes/hour), or failure to take ORS for any reason"
- Duration of IV rehydration for the entire treatment period per treatment group and per each 24-hour period of treatment.
- Number of recovered subjects within treatment group. The number of recovered subjects will be recorded as total for the entire treatment duration, and as number of recoveries per each 24-hour period of treatment.
- Safety will be measured by the proportion of patients that will present with AE following administration of VR-AD-1005.

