6.4. Safety Analyses

Safety analysis is not the primary or secondary objective of this study, thus safety will be analyzed as summary statistics during treatment. AEs will be coded per Medical Dictionary for Regulatory Activities (MedDRA), and calculated. Each AE will be counted once only for a given participant, and presented using standard available criteria for severity, frequency, and relationship of AEs to study intervention. Start date, stop date, severity, relationship, expectedness, outcome, and duration will be reported for each SAE. Adverse events leading to premature discontinuation from the study intervention and serious treatment-emergent AEs will be listed. Proportion of the patients presented with AE or SAE will be calculated for IP and Placebo arms as a fraction of the total number of participants per arm and expressed as percent. Percentage of AE and SAE occurrence will be compared between IP and placebo groups to provide information regarding the safety of the investigational product.

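### Section 6.4 divides AE and SAE patients by the whole arm, no dosed, as-treated safety set is defined, and other sections could drop dosed patients

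*Combined protocol and SAP*

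**What the plan says.** Section 6.4 expresses AE and SAE occurrence in each arm "as a fraction of the total number of participants per arm and expressed as percent" and compares the percentages between arms. The endpoint in section 6.0 reads "Safety will be measured by the proportion of patients that will present with AE following administration of VR-AD-1005"; Table 1 in section 5.0 words it similarly and adds SAEs.

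Sections 6.2.1 and 6.3 name ITT, MITT and PP groups for the efficacy endpoints. Section 6.1, despite its title, lists comparisons and not populations. No safety population appears anywhere.

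Four other places bear on who would be counted:

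- Section 4.11: "Subjects who sign the informed consent form and are randomized but do not receive the study intervention may be replaced". It does not say whether the replaced patient stays in any denominator.
- Section 4.4.6.1: arms are assigned from the randomisation tables, and "data from all participants who have completed the trials will be assigned to the Group A" or to Group B.
- Section 4.3: enrolled patients whose culture is negative stop treatment and are left out of the final analysis. Results are expected by day three. No exception is made for safety.
- Section 5.0: the allowance for lost power mentions "data points lost due to participant drop-out, cross-over to other study arms, withdrawal and missing data".

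**The concern.** The numerator and the denominator in 6.4 cover different people. An event can follow administration only in someone who was dosed, and Appendix I records AEs only from hour 0. A randomised, undosed patient therefore adds to the denominator and hardly to the numerator.

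Such patients are possible. Section 4.3 states "Patients will receive their first dose administered by the study nurse immediately after the consenting process and randomization is completed", but section 4.5.1 says "Initiate IP administration as soon as participants can tolerate oral intake", and Appendix I places randomisation in the screening column (hour −4) and the first dose at hour 0. All patients have severe dehydration on arrival, so some gap between randomisation and first dose can occur.

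Grouping from the randomisation tables also means that, if a patient were given the wrong product, the AEs would be attributed to the product not taken.

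The other passages carry the opposite risk. Limiting the analysis to completers, or to culture-positive patients, would remove people who were exposed, together with any AEs they had. At stake is whether the AE and SAE percentages describe the patients who took each product, and whether the choice among several possible denominators is left until after unblinding.

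**Working it through.** The documents give no AE rate, no number undosed and no number given the wrong product, so there is no safety figure of the plan to reproduce. The one documented input is the arm size: patients are "randomized to intervention and placebo groups with 75 patients per group" (section 4.0). Everything else below is an assumption, shown over a range.

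**1. Dilution by undosed patients.** Assume a true AE rate of 20% among dosed patients and k undosed patients counted in the arm. If they are not replaced, the arm holds 75 with 75 − k dosed. If they are replaced but still counted, it holds 75 + k with 75 dosed.

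| k | Not replaced: 0.20 × (75 − k)/75 | Replaced, still counted: 0.20 × 75/(75 + k) |
|---|---|---|
| 2 | 0.20 × 73/75 = 19.5% | 0.20 × 75/77 = 19.5% |
| 4 | 0.20 × 71/75 = 18.9% | 0.20 × 75/79 = 19.0% |
| 8 | 0.20 × 67/75 = 17.9% | 0.20 × 75/83 = 18.1% |

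**2. Effect on the comparison.** With the same k in both arms, both rates are multiplied by the same factor: the risk ratio is unchanged and the risk difference shrinks. For k = 4, assumed rates of 20% and 10% become 18.9% and 9.5%; the ratio stays 2 and the difference falls from 10.0 to 9.5 points (10.0 × 71/75). With unequal k the bias can go either way. Four undosed on active and none on placebo turn equal true rates of 20% into 18.9% v 20.0%; the reverse split gives 20.0% v 18.9%.

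**3. Wrong product, counted as randomised.** Assume true rates of 20% and 10% and m patients swapped each way.

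- m = 2: (73 × 20% + 2 × 10%)/75 = 19.7%; (73 × 10% + 2 × 20%)/75 = 10.3%; difference 9.5 points.
- m = 4: (71 × 20% + 4 × 10%)/75 = 19.5%; (71 × 10% + 4 × 20%)/75 = 10.5%; difference 8.9 points.

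A true difference of 10.0 points is pulled towards zero.

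**4. Loss of dosed patients.** Suppose 75 were dosed and 15 had an AE: 15/75 = 20.0%. Remove d = 3 dosed patients, a of whom had an AE; the rate becomes (15 − a)/(75 − d).

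- a = 3, for example three patients withdrawn because of AEs: 12/72 = 16.7%.
- a = 0: 15/72 = 20.8%.

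The first case is relevant to a completers-only reading. Section 4.11 allows withdrawal for AEs or SAEs, section 4.4.6.3 withdraws patients whose code is broken, and section 4.6 defines completion as having gone through all scheduled phases. For culture-negative patients neither the number nor the AE rate can be derived from the documents.

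**5. The readings side by side.** Section 6.4 gives everyone in the arm; 4.4.6.1 gives completers; 4.3 gives everyone except culture-negative patients; 4.11 leaves open whether replaced patients count. These are different denominators, and nothing says which applies to safety.

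**The case against.** The strongest reply is that 6.4 never mentions undosed patients. Its whole-arm wording is loose, other sections point to narrower groups, and 4.11 only permits replacement without predicting that any patient goes undosed. Dosing is nurse-administered to inpatients from individually numbered packages, and is planned straight after randomisation, so few patients are likely to go undosed or receive the wrong product. Section 6.4 also requires listings of serious treatment-emergent AEs and of AEs leading to discontinuation, so individual serious events should remain visible. All of this stands. It limits the likely size but does not supply the missing definition.

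Three stronger readings are tempting, and the documents do not support them:

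- *Undosed patients must be counted because nobody is subtracted after randomisation.* That rule, in 6.2.1 and 6.3, concerns the ITT group for efficacy; 6.4 does not invoke ITT.
- *The errors make the active product look safer.* Undosed patients dilute both arms. Equal numbers leave the risk ratio unchanged, unequal numbers can favour either arm, and double-blind packaging gives no reason to expect more undosed patients on active. Swaps shrink whatever true difference exists, which favours the active product only if it truly raises AE rates.
- *Wrong-product dosing is expected.* Cross-over in 5.0 is one item in a general list of threats to power; no rate or mechanism is given.

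**Conclusion.** The point holds as a defect in the stated method. The denominator in 6.4 does not match the endpoint, no at-least-one-dose set grouped by product received exists, and 4.3, 4.4.6.1, 4.11 and 6.4 cannot all describe the same safety population. Safety and tolerability are listed among the secondary objectives in Table 1, so the population should be fixed in advance.

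The dilution is probably small: about 1 percentage point (20.0% to 18.9%) at an assumed 20% rate with 4 of 75 undosed, and about 2 points with 8. Its direction between arms is unknown. The loss of dosed patients under the completer or culture-positive readings could be larger, but its size cannot be estimated from the documents. All sizes rest on assumed AE rates and counts; only the 75 per arm comes from the plan.

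**What to change.** In section 6.4, replace the whole-arm denominator with: *all randomised participants who received at least one dose, grouped by product actually received, regardless of culture result or completion*. Use it for both AE and SAE percentages.

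Then reconcile the other sections:

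- In 4.3 and 4.4.6.1, state that leaving out culture-negative patients and non-completers does not apply to the safety analysis.
- In 4.11, state that randomised patients who were never dosed, whether or not they are replaced, are outside the safety set. Their place in the ITT group for efficacy is unaffected.

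The cost is a few sentences. No new data are needed: dosing times, package numbers and AEs are already recorded, and 4.11 already calls for AE assessment when treatment is discontinued. The only downside is a small change in the stated AE percentages.

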6.5. Other Analyses

In addition to the overall analysis of the intervention vs. placebo, it is important to elucidate the efficacy of the IP as a function of the severity of the diarrheal disease. Thus, participants will be segregated into three subgroups based on the volume of stool output. All subgroups will be analyzed using both ITT and PP populations. moderate subgroup (stool volume 3-8 liters per 24 hours) and severe subgroup (stool volume >8 liters per 24 hours). Subgroups are intended for analytical purposes and will not affect randomization. Within the subgroups the analysis will be performed as above.

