6.0 Data Analysis

Describe plans for data analysis, including stratification by sex, gender and diversity. Indicate whether data will be analysed by the investigators themselves or by other professionals. Specify what statistical software packages will be used and if the study is blinded, when the code will be opened. For clinical trials, indicate if interim data analysis will be required to determine further course of the study.

Data analysis must comply with ICH E9 Guideline and ICH E9(R1) Guideline. All relevant data collected in the trial should be considered in the statistical considerations section.

The analysis will be conducted on all participant data at the time the trial ends.

Statistics for primary end-point data and parametric secondary end-point data will be presented via means (alternatively, LSMEANS) with standard deviations; primarily two-tailed Student's t-test will be used for analysis with significance level of $p \leq 0.05$. For non-parametric analysis, such as lifetime data, Kaplan-Meier analysis will be used with significance level of $p \leq 0.05$. Some data might be expressed and analyzed as % values, such as the occurrence of unscheduled IV rehydration.

Analysis of secondary endpoints will be performed through the same method of the primary endpoint, which is found via a one- sided two sample unequal variance Student's t-test. The scale for each secondary endpoint will be nominal and will be determined at a single endpoint, which is at the end of intervention. The results will be presented by LSMEANS (Least-squares Means) with standard errors.

Primary Endpoint:

Reduction in stool output volume (ml/hour) over a treatment period measured and plotted as total stool output during 12-hour stool collection at every 12 hours for 72 hours.

Secondary Endpoints:

- Time until the stool volume output of 200mL/hour or less. Duration of stool output in excess of 200mL/hour per patient will be recorded between the start and end of the treatment for both treatment groups.
- Time until recovery. Duration of diarrhea until the passage of first non-watery stool or no stool for 12 hours or the end of treatment (72 hours) will be derived from date and time records in daily stool charts.

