6.2. Analysis Supporting Primary Objectives

6.2.1. Statistical Model, Hypothesis, and Method of Analysis

Primary Endpoint:

Reduction in stool output volume over a treatment period.

Primary Endpoint 1., Hypothesis 1. Treatment with VR-AD-1005 reduces stool output in patients with diarrhea due to *V. cholerae* infection. Null hypothesis is stated as no statistically significant difference in stool output volume as compared to placebo; alternative Hypothesis 1 is stated as statistically significant reduction in stool output volume in patients treated with VR-AD- 1005.

Two analytical approaches are proposed. Approach 1 will be based on the total quantity of stool purged by participant during the intervention administration period. Stool output will be expressed as g/kg body weight based on the stool charts, and the means will be compared between intervention and placebo groups using Student's unpaired t-test. In approach 2, stool purging is measured and plotted as total stool output in ml/kg/12 hours based on the individual stool collection charts. Weight of stool will be converted to volume using 1:1 weight/volume ratio. Diarrhea of cholera resolves rapidly, and majority of patients are expected to recover within 30-50 hours after randomization. 12-hour analysis increments allow a better insight into the onset and timing of the effect of study intervention as compared to cumulative data over the duration of the treatment. Means will be compared for each 12-hour period after first intervention administration using unpaired Student's t-test. Normal distribution is assumed for both cases. Analysis will be conducted in the ITT, MITT and PP groups. Missing data and outliers will be handled using imputation technique. Non-adherence and lost to follow-up patients will be categorized into the appropriate group and handled accordingly. No subtractions will be made from the ITT group after randomization assignment.

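### Section 6.5 asks whether efficacy depends on disease severity but only repeats the tests inside each severity subgroup, with no comparison of the treatment effect between subgroups

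*Combined protocol and SAP*

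**What the plan says.** Section 6.5 (Other Analyses) gives its purpose as: "it is important to elucidate the efficacy of the IP as a function of the severity of the diarrheal disease". It then says that "participants will be segregated into three subgroups based on the volume of stool output", gives limits for a "moderate subgroup (stool volume 3-8 liters per 24 hours) and severe subgroup (stool volume >8 liters per 24 hours", and adds that "All subgroups will be analyzed using both ITT and PP populations". The method is one sentence: "Within the subgroups the analysis will be performed as above".

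The analyses above it are these:

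- Section 6.2.1: a t-test on total stool output in g/kg, and a second approach in which "Means will be compared for each 12-hour period after first intervention administration using unpaired Student's t-test". Table 1 expects six such periods in 72 hours.
- Section 6.3: t-tests for rehydration and for time above 200 ml/hour, and Kaplan-Meier curves for duration of diarrhea.
- Section 6.0: for the primary and parametric secondary endpoints, "primarily two-tailed Student's t-test will be used for analysis with significance level of" 0.05. The same section also describes the method for the endpoints as one "which is found via a one- sided two sample unequal variance Student's t-test".

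No section names an interaction term, a multiplicity rule for subgroups, an expected subgroup size or an exploratory label. ANCOVA appears only in the list of abbreviations.

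**The concern.** Whether efficacy varies with severity is a question about effect modification: is the treatment difference in one severity group different from that in another? Separate tests inside each group ask something else, namely whether each group on its own shows a difference from zero. Each subgroup has fewer patients than the trial, so its test has less power. One p-value can fall below 0.05 and another above it by chance while the true effect is the same in both.

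This is a phase II trial, and its subgroup results may inform the population of a later one. Discordant subgroup p-values invite the reading that the drug works only in severe, or only in moderate, cholera. If the overall test fails, the subgroup repeats also give many unadjusted chances of an apparent benefit. Stool output alone has seven tests per subgroup (one total, six 12-hour periods) in each of two analysis sets. That is 7 × 2 × 2 = 28 tests with two subgroups and 7 × 3 × 2 = 42 with three, before any secondary endpoint.

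**Working it through.** **Inputs.** Section 5.0: mean 280 g/kg, SD 156, 33% reduction, two-sided alpha 0.05. Section 4.0: 75 per arm. The effect is 0.33 × 280 = 92.4 g/kg, so d = 92.4/156 = 0.592. The plan gives no subgroup sizes and no within-subgroup SDs; those below are assumptions.

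**Plan's own figure.** Power comes from the noncentral t distribution with 2n − 2 degrees of freedom and noncentrality d × √(n/2). At 50 per arm it is 0.835 (plan: 0.82) and at 75 per arm 0.950 (plan: 0.94). Both agree within 2 percentage points.

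**Uniform absolute effect, full SD of 156 in each subgroup, severity unaffected by treatment.** The chance of significance in some but not all subgroups is 1 − ∏(power) − ∏(1 − power).

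- Two equal subgroups (37.5 per arm): power 0.716 each; 1 − 0.716² − 0.284² = 0.407.
- Subgroups of 25 and 50 per arm: powers 0.537 and 0.835; 0.537 × 0.165 + 0.463 × 0.835 = 0.475.
- Three equal subgroups (25 per arm): power 0.537 each; 1 − 0.537³ − 0.463³ = 0.746.

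In the equal-subgroup scenarios a simulated interaction test at 0.05 was significant 5.2% (two) and 4.7% (three) of the time.

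**Sensitivity.**

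| Change in assumption | Two subgroups | Three subgroups |
|---|---|---|
| Within-subgroup SD 0.8 × 156 | 20% | 59% |
| Within-subgroup SD 0.7 × 156 | 9% | 41% |
| Unequal sizes, full SD | 43-77% | 77-87% |
| True reduction 20% | 45% | 54% |
| True reduction 10% | 21% | 25% |
| Lognormal output, uniform 33% proportional effect, baseline severity correlated 0 to 0.7 with output | 23% down to 8% | 64% down to 28% |

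The last row uses a lognormal with mean 280 and SD 156, so the log variance is ln(1 + (156/280)²) = 0.270.

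**No effect, one endpoint.** At least one false subgroup result: 1 − 0.95² = 0.0975 with two subgroups and 1 − 0.95³ = 0.143 with three.

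**Scale of the interaction.** Under the same lognormal model with a uniform 33% reduction, an interaction test on raw g/kg rejects about 14% of the time at correlation 0.5 and about 28% at 0.7. On the log scale it rejects about 5%. A constant percentage effect is a larger absolute effect where output is higher, so the raw scale reports a difference that the ratio scale does not.

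**Power of the interaction test.** With two equal subgroups, the standard error of the difference between subgroup effects is 156 × √(4/37.5) = 50.9 g/kg. For 80% power the true difference would have to be about (1.96 + 0.84) × 50.9 = 143 g/kg, or 143/92.4 = 1.5 times the whole planned effect.

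**The case against.** The strongest reply is that the section is plainly supplementary. It sits under other analyses, adds to the overall comparison, and has no counterpart objective in Table 1. It nowhere says that significance in one subgroup and not another will be read as dependence on severity. That stands: a reader might take the chance of discordant p-values to be the chance of a false conclusion, and the documents do not support that step. What remains is that the stated question has no stated method that could answer it.

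A reader might also quote 41-75% as the error rate of the plan. That is not supported either. The range needs equal subgroups, a constant absolute effect and the full SD in each. Subgroups are cut on stool volume, which is close to the outcome itself, so the SD within them is probably below 156, and the planned effect is a percentage. Both pull the figure down; unequal sizes push it up. The upper end needs three subgroups, and limits are legible for only two. Text may have been lost in extraction there, so nothing is made of the missing limits.

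A third tempting reading is that severity is classified on treatment. The limits are per 24 hours, screening is at hour −4 (Appendix I) and efficacy stool collection starts after the first dose (section 4.5.2), but the plan does not say when the grouping volume is measured. The ambiguity still matters: an interaction with a variable that the drug can change is not interpretable, so the remedy must settle the timing.

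The one-sided and two-sided statements in section 6.0 conflict. That is a separate matter and does not alter this point.

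**Conclusion.** The point holds in a limited form. Following section 6.5 as written cannot show whether efficacy depends on severity, because no analysis compares treatment effects between severity groups. That conclusion needs no numerical assumption.

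The size does. On the plan's own effect and SD, with equal subgroups, 75 per arm and total stool output only, a uniform effect gives discordant subgroup results about 41% (two) or 75% (three) of the time, against about 5% for an interaction test. Smaller within-subgroup SDs or a uniform proportional effect give roughly 8-23% and 28-64%. These are illustrations, not bounds. With no drug effect, a single endpoint yields a false subgroup result 9.75% or 14.3% of the time.

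The primary analysis is not affected. The plan should be changed because the severity conclusion would otherwise be unsupported.

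**What to change.** In section 6.5, replace "Within the subgroups the analysis will be performed as above" with text to this effect:

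*Severity groups will be defined from information recorded before the first dose. Total stool output (g/kg, ITT) will be modelled on treatment, severity group and their interaction on a log (ratio) scale, matching the planned percentage reduction, with the absolute scale as a sensitivity analysis. The interaction is the only subgroup test and is exploratory. Subgroup treatment effects will be shown with 95% confidence intervals, without subgroup p-values or efficacy claims. Subgroup repeats of the 12-hour and secondary analyses are descriptive.*

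Two details need settling with it. The grouping limits are per 24 hours, so they must be tied to something available before dosing. The model also needs a rule for any patient with zero output, for example a log link instead of a log transform.

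The cost is SAP wording and one regression model, with no added patients or visits if the severity measure is already recorded at screening. The downside is the low power shown above: the result will be an estimate with a wide interval, and a non-significant interaction will not show that the effect is uniform.
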